Completed the study	Reported at the end of the trial: Participants who completed the 12-month assessment with a body weight report. Individuals who participated in the 12-month assessment but did not have an objective report of their body weight were determined as “Assessment Incomplete”.	Complete the form after incentives distribution. Inactive mLife account (do not remove the link to FitBit)
---------------------	---	---

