### **Sample size according to F-test**

Because our main outcomes will be measured at 12 months, we are using pilot work that collected weight loss outcomes at one year. Based on our pilot data (NETworks trial as this provides 12-month outcomes for weight), as well as several other one-year mHealth intervention studies, we calculated the sample size necessary to achieve 95% power (alpha = 0.05) for Aim 1 assuming a small effect size (Cohen's  $d = 0.1$ ) and an intra-cluster correlation (ICC) equal to 0.7. The sample size estimate was 200. For this calculation, we used an F-test on the interaction between time (two levels) and treatment arm (two levels) in a two-way ANOVA with repeated measurements (RM-ANOVA). We used a more conservative value of the ICC as compared to the actual estimate from the NETworks trial data (ICC = 0.9), as the latter would have resulted in a much smaller sample size (for a larger ICC, the residual sum of squares decreases, therefore precision increases and sample size decreases. The opposite is true when the test is strictly between subjects). Further, we assumed an attrition rate between 15 and 20%, and increased the sample size to 240. Thus, we aim to recruit a total of 240 participants (~120 per cohort), with the initial randomization assigning 120 to SocialPOD+points and 120 to SocialPOD-points.

Based on pilot study for overall app usage (Social POD  $50.7 \pm 25.0$  days and standard  $34.4 \pm 25.8$  days out of a possible 84 days) and points earned (mean of  $202 \pm 105$  points/participant with estimated 50 point difference between groups), our power for Aim 2 will be 99% for app usage and 95% for points earned based on our sample size from Aim 1.

We plan to use a random-effects (RE) model which is mathematically equivalent to repeated-measures-ANOVA. However, in the presence of loss to follow-up, RE models can handle responses that are missing at random. RE models can be adjusted for additional covariates if needed (though the randomization procedure should make this unnecessary). RE models provide additional information about the variance of the random effects which is valuable for understanding heterogeneity of responses and assessing the intra-cluster correlation (ICC).

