### **III. Below describes our plans for interim and final analyses and methods for handling missing data:**

#### ***Aims 1 and 2***

Data from all study measures will undergo initial data cleaning to identify potential outliers, determine distributions of variables, assess normality, and enumerate loss to follow-up and other missing data. Descriptive statistics at baseline will be compared between treatment groups to evaluate the success of randomization. ***Analyzing changes in weight between groups at year one***

***(Primary Aims 1):*** For Aim 1, the two levels of the treatment effect will be assignment to SocialPOD+points vs. SocialPOD-points, and the entire study sample will be included. Primary Aim 1 will be addressed using a repeated-measures mixed model with maximum likelihood estimation as provided by PROC MIXED in the SAS® system. Under the assumption that missing data are missing at random, mixed models provide unbiased estimates. These will be adjusted using robust computation of standard errors if non-normality is detected. These models will be estimated applying an intent-to-treat principle. Models for each primary aim are of the same form, with the difference of the groups being compared. Models will examine weight at baseline and at 12 months with a two-level time effect, two-level treatment effect, and two-way interaction between time and treatment. The repeated-measures model will contain time, treatment, time-by-treatment interactions, and any covariates associated with weight loss. Models will be adjusted for changes in PA (via

accelerometers). If the time-by-treatment interaction in a model is significant at the 0.05 level, this will be interpreted as a significant weight-loss effect for one treatment relative to the other.

**Analyzing differences in social support provision and receipt between groups (Aim 2):** For Aim 2, the model will regress support provided (total points earned) and social support received (mean of ratings of support provided to the individual over the 12 months) on treatment group, adjusted for the same covariates used in Aim 1.

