#### IV. Below details various types of bias and how our study aims to avoid them.

Type of Bias	How to Avoid
Pre-trial bias	
Flawed study design	We have a clearly defined risk and outcome and are using objective or validated methods. Standard operating procedures will be developed for data collection and assessors will be blinded to random assignment.
Selection bias	We will select participants using rigorous criteria to avoid confounding results. Participants will originate from the same general population. Because this is a well-designed, prospective study, selection bias should be avoided as outcome is unknown at time of enrollment.
Channeling bias	We will assign participants to study cohorts using rigorous criteria, stratifying by sex and race.
Bias during trial	
Interventionist bias	All study personnel interactions with participants will be standardized. As part of our treatment fidelity process, interactions with participants (e-mails, phone calls, etc.) will be regularly assessed and monitored to assure equal treatment among groups.
Recall bias	We will use objective data sources whenever possible. While surveys and the dietary recalls will rely on memory, these measures are currently the gold-standard way to assess these outcomes.
Transfer bias	We will carefully design plan for lost-to-follow-up participants prior to the start of the study. This will include number of contacts required after a participant does not attend classes or assessment visits.

Outcome Misclassification	We are using objective validated measures to assess all primary outcomes.
Bias after trial	
Citation bias	Our trial will be registered with clinicaltrials.gov prior to study recruitment for cohort 1. We will check registries for similar unpublished or in-progress trials prior to publication.
Confounding	Known confounders will be controlled during data analysis (such as medications). Unknown confounders will be controlled with randomization.

\* Adapted from Pannucci CJ, Wilkins EG. *Plast Reconstr Surg.* 2010 Aug; 126(2): 619–625.

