## V. Consideration of relevant biological variables

Of primary interest in the present study will be examining differences in outcomes by sex and age. Previous research has demonstrated that men lose more weight than women in behavioral weight loss interventions, but there is no indication that different weight loss strategies should be used. There is evidence that men may interact with technology, including health-related mobile technology, differently than women. For example, a study examining gender differences in usage of a physical activity app found that enjoyment and goal-setting were more important for women than men but that men more often shared their results and used the live tracking function in the app. Other research has found that men feel that mobile phone usage is more appropriate across a variety of social situations than women. In addition, those under 50 (and particularly those under 30) tend to have higher rates of smartphone ownership than those over 50. Based on these findings, we aim to conduct sub-analyses examining the impact of sex and age on social support provision and receipt and weight loss. We have been successful recruiting both men and AA participants in our previous studies and being situated in South Carolina and housing this work within the Prevention Research Center (where the current main research project is among AA churches in SC) will ensure we can consider both of these relevant biological variables. Our models will also control for other factors that could impact outcomes, including age, BMI, SES, baseline lab values, and medication use.

**A. Below details our approach to data management and validation, including our data management system, methods of data entry and cleaning, and event tracking and logistics**  
 [name], Project Manager, and [name], study PI, will develop and maintain the computerized data management system for this study. Use of the data management system will be restricted to only those persons having access authority.

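### The Aim 1 and Aim 2 models must adjust for change in physical activity, which is measured after randomisation, and no rule covers missing values

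*Combined protocol and SAP*

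**What the plan says.** The analysis plan for Aims 1 and 2 tests Aim 1 with a repeated-measures mixed model of weight at baseline and 12 months. The time-by-treatment interaction is judged at the 0.05 level under intent-to-treat, "and the entire study sample will be included". Besides time, treatment and their interaction, the model takes "any covariates associated with weight loss". The plan then adds: "Models will be adjusted for changes in PA". The Aim 2 regressions on treatment group are "adjusted for the same covariates used in Aim 1", so the PA term carries over.

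Other sections bear on this:

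- **PA as target and outcome.** Study Intervention names PA as a behaviour the programme works on. The Assessments table lists it among potential drivers of weight loss.
- **PA measurement.** The Physical activity section takes PA from the Fitbit at Weeks 0, 26 and 52, requires three valid days, and allows data from two weeks before or one week after. It says nothing about PA still missing after that.
- **Completion.** A study completer is defined by weight alone: "Participants who completed the 12-month assessment with a body weight report".
- **Other covariates.** The section on biological variables says: "Our models will also control for other factors that could impact outcomes, including age, BMI, SES, baseline lab values, and medication use". The table of biases adds medications as confounders to control. The sample size section treats adjustment as optional and expects randomisation to make it unnecessary.

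**The concern.** Hypotheses 1 and 2 ask whether being given points produces more weight loss and more social support. Those are total effects. Change in PA is observed after allocation and could lie on the path from points to weight. Adjusting for it can change the question being tested.

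The sentence does not fix the form of the term. It does not say whether change runs to Week 26 or Week 52, or whether it enters as a main effect, by time, or as a time-varying value. These choices can give different primary estimates from the same data.

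A covariate from a wearable also brings its own missing data. The plan's missing-at-random argument protects against missing responses, not missing covariates. A participant with a valid 12-month weight could leave the primary analysis for lack of tracker days.

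The rest of the covariate set is open as well. It can be chosen after seeing what is associated with weight loss. Socioeconomic status and medications are collected at baseline, 6 and 12 months, so post-randomisation values could enter.

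**Working it through.** **1. The plan's own figure.** Inputs from the sample size section: effect size 0.1, ICC 0.7, two time points, two arms, alpha 0.05, N = 200. The label is Cohen's d, but 200 reproduces only if 0.1 is read as Cohen's f.

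- Noncentrality: λ = N·f²·m/(1 − ICC) = 200 × 0.01 × 2/0.3 = 13.33. Power on 1 and 198 df is 95.3%.
- In SDs of weight change, with 100 per arm: δ = √(13.33/50) = 0.516.

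This calculation contains no PA term.

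**2. Aim 1, by form of the PA term.** With two time points and complete data, the interaction is the between-arm difference in mean change. A covariate that is constant within a person cancels from that change. As a main effect, then, PA change leaves 0.516 as it is and gains no precision. If it enters by time, with a points effect on PA of s SDs and a correlation r between PA change and weight change:

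- estimate = 0.516 − s·r
- power at 100 per arm, with residual SD √(1 − r²) and variance inflation 1 + s²/4

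| s | r = 0.2 | r = 0.3 | r = 0.4 |
|---|---|---|---|
| 0 | 0.516 (96.0%) | 0.516 (96.8%) | 0.516 (97.7%) |
| 0.1 | 0.496 (94.5%) | 0.486 (94.7%) | 0.476 (95.4%) |
| 0.2 | 0.476 (92.6%) | 0.456 (91.8%) | 0.436 (91.5%) |
| 0.4 | 0.436 (86.7%) | 0.396 (81.8%) | 0.356 (76.5%) |

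For s of 0.2 to 0.4, the loss runs from 0.04/0.516 = 8% to 0.16/0.516 = 31%. If points lowered PA by 0.2 SD (r = 0.3), the estimate would rise to 0.576, or 12% larger. In kg, with an assumed SD of change of 4.65 kg, the planned effect is 0.516 × 4.65 = 2.40 kg. Removing a 30% share leaves 0.7 × 2.40 = 1.68 kg. Both scale in proportion to the assumed SD.

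A simulation of 400,000 participants (s = 0.4, r = 0.387, a 30% share through PA) gave:

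- no PA term: −0.519
- main effect: −0.519
- PA by time: −0.362
- time-varying PA: −0.407

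With s = 0 and r = 0.3, all four lay between −0.520 and −0.521.

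**3. Aim 2.** There is no time term, so PA change acts directly on the group coefficient. From the planned 50 points (SD 105), the adjusted difference is 50 − 105·r·s:

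- r = 0.1, s = 0.2: 50 − 2.1 = 47.9
- r = 0.3, s = 0.4: 50 − 12.6 = 37.4
- s = 0: 50

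**4. Missing PA.** A weight without valid PA is foreseeable for four reasons: completion needs only a weight, a scale photo can supply one, assessment-only participants stay in follow-up, and valid PA days are a separate component of the incentive. By default PROC MIXED drops rows with a missing covariate.

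- *Missing at random:* if 10%, 20% or 30% of 200 completers lack PA, 90, 80 or 70 per arm remain. Power is 93.1%, 90.1% or 85.9%, with no bias.
- *Missing more often with poorer weight change, by one logistic rule in both arms:* at an odds ratio of 1.65 per SD, missingness is 16.1% (points) v 19.7% (mLife) and the estimate is 0.500 (3% smaller). At 2.72 it is 17.3% v 24.6% and 0.460 (11% smaller). With only about 7% to 11% missing, the same rules give about 1.5% and 6%.
- *Baseline-only rows of those lost to follow-up:* dropping these too raises the interaction variance by only 2.3% to 3.1%.

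**The case against.** The strongest reply is that the listed model terms include no PA-by-time term. Read literally, PA change is a main effect and cannot move the Aim 1 interaction when data are complete. Distortion then needs a form the plan does not state and an effect of points on PA that no section reports. Both arms receive the same PA advice, and a participant's own activity earns no points. With a shift of only 0.1 SD, power stays at 94.5% to 95.4%. All of this stands, and it makes the Aim 1 bias conditional.

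The missing-PA figures are also assumptions. Weight and PA usually sync through the same account, so a participant who stops syncing may lose both, and the true rate of weight without PA could be low. That stands too. The analysis section also says the PA comes from accelerometers, while the Physical activity section specifies a Fitbit tracker, so applying the Fitbit valid-day rules to this covariate is an inference.

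The reply does not rescue the sentence. In the harmless form, the term adds nothing to the Aim 1 test and can still exclude people with a weight. In the other forms, it can change the effect being estimated. In Aim 2, the main-effect form already conditions on a post-randomisation variable.

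**Conclusion.** The concern holds. The plan requires a post-randomisation covariate in the Aim 1 model and in the Aim 2 regressions, leaves its form open, and has no rule for values still missing after the fallback window.

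Two defects are present whatever the data show: the form is unspecified, and a missing covariate conflicts with the commitment to intent-to-treat and the full sample. The second rests on default PROC MIXED handling.

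Bias in the estimate is conditional. It requires that points affect PA and, for Aim 1, that the term is fitted with time; separately, it can arise if missing PA is related to weight change. The sizes above illustrate those conditions. They do not predict what this trial will show, because the documents give no effect of points on PA, no correlation of PA change with weight change, and no rate of missing PA. The point should be fixed; it does not undermine the design or the sample size.

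**What to change.** 1. Delete the sentence on changes in PA from the Aim 1 model, which also removes it from Aim 2.
2. Replace the open covariate wording with one pre-named list of baseline values: the randomisation stratification factors, cohort, age, baseline socioeconomic status and baseline medication. First reconcile the factors, since Overview of assessments gives sex and BMI while Randomization Procedure gives race and sex. Baseline weight is already a response in the model, so use BMI only if it proves to be a stratification factor.
3. Make the table of biases and the section on biological variables match. Specify baseline values for socioeconomic status and medication. Identify the baseline lab values or remove them, as the Assessments table lists none.
4. State the form of each covariate and how a missing baseline value is handled, for example with a missing category, so that nobody with a weight is omitted.
5. Add change in PA as a secondary mediation analysis under Secondary Aims, with its own definition, form and missing-PA rule.

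The cost is wording. The repeated-measures model, the test and the sample size stay as they are, and the mediation analysis uses data already collected. The primary model gives up any residual variance PA change would explain: 4% to 16% at r = 0.2 to 0.4 (r² = 0.04 to 0.16). That means power of 95% instead of 96% to 98%, and only if the term had been fitted by time. The change alters a prespecified primary model, so it should be made and dated before group assignments are unblinded for analysis.

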#### Primary aims:

**Aim 1:** Determine if the mLife app plus points intervention (mLife+points; points for provision and receipt of social support) produces significantly more weight loss at 12 months than the mLife without points (mLife) among 240 adults with overweight or obesity and  $\geq 3$  T2DM risk factors.

Hypothesis aim 1: The mLife+points group will lose more weight than the mLife group.

**Aim 2:** Examine the differences in social support provision and receipt

between groups at 12 months.

Hypothesis aim 2: That the mLife+points group will have greater levels of social support provision and receipt (both perceived and received) than the mLife.

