## Assessments

Participants' assessments will be conducted at baseline, 6, and 12 months of the intervention. The following table and cited references describe the surveys and measurements conducted at each time point:

Instrument	BL	6 mo	12 mo
Demographic, social support and potential mediators/moderators			
Demographic and socioeconomic status			
Demographic variables	X		
Socioeconomic status variables, use of nutrition assistance programs, environmental changes	X	X	X
Current medications	X	X	X
Social support provision, receipt and enjoyment			
Number of times a person completes a social support-related activity (SS provision)		X	X
Adapted Multidimensional Scale of Perceived Social Support Scale (MSPSS) – (SS perceived) 		X	X
Ratings each participant gives to the social support provided to them after they request support (SS perceived)		X	X
Total number of times other participants provided support to the individual (SS receipt)		X	X
EGameFlow (enjoyment) 		X	X
User engagement and user burden			
User Engagement Survey* (adaptation) 	X	X	X
User Burden Scale* (adaptation) 	X	X	X
Self-efficacy and -regulation and motivation			
Weight Efficacy Life-Style Questionnaire (WEL-Q) 	X	X	X
Treatment Self-Regulation Questionnaire (TSRQ) 	X	X	X
Potential drivers of weight loss			
NCI's Automated Self-Administered 24-hour Dietary Recall (ASA24®) – 3 unannounced recalls – two weekdays, one weekend day) 	X	X	X

Physical Activity (FitBit tracker) – minutes per week of MVPA (min:10h/d, 3 valid days) 	X	X	X
Exercise Vital Sign Questionnaire 	X	X	X
The Stanford Leisure-Time Activity Categorical Item (L-Cat), short version 	X	X	X
Physiological and anthropometric measures			
Height (self-report) / weight (FitBit Aria Scale) 	X	X	X
Hip and Waist circumference (self-report).	X	X	X
T2DM (Type 2 Diabetes Mellitus) risk factors (risk score 0 – 10)	X	X	X
Self-monitoring adherence and study compliance/responsiveness			
Monthly survey (self-monitoring)		X	X
Adherence to FitBit devices usage (mLife app – rewards or points)		X	X
Adherence to self-monitoring diet (mLife app - logging $\geq 2$ eating occasions per day)		X	X
Use of intervention components (mLife app - use of all intervention components)		X	X
Factors that may affect compliance: differential dropouts and reasons to discontinue the study		X	X

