## Intervention components procedures

Both groups will receive the same intervention, but to isolate the impact of points/social gaming, the mLIFE+points group will receive points for engaging in social support-related behaviors, and the mLIFE will not. The intervention components and points system is displayed below.

Intervention Components	Points
Podcasts (within the app):	
Nutrition and exercise information	N/A*
Audio diary	N/A
Goal setting	N/A
mLIFE app:	
Self-regulation features	
Diet, PA**, and weight tracking app components	N/A
App notifications at specific times to remind participants to self-monitor	N/A

Newsfeed of activity listing when someone self-monitored diet, PA, and weight; downloaded a podcast or read a tip of the day; or requested social support on a topic.	N/A
Leaderboard and Points tracker	N/A
Social support features	
Thumbs Up that someone tracked their diet for the day (posted to newsfeed)	1
Thumbs Up a notification that someone logged 30 min of PA for the day (posted to newsfeed)	1
Thumbs Up a notification that someone logged their weight for the day (posted to newsfeed)	1
Thumbs Up a notification that someone listened to a podcast or read a tip of the day (posted to newsfeed)	1
Sending someone an encouraging message when they have not logged on (choice of 3 pre-populated messages or ability write their own message)	1
Sending out a request for help on a specific topic related to diet or PA	1
Responding to a request for help	1
Thanking someone for a thumbs up or response to a request for help (participants will also rate how supported they felt for each response they receive)	1
Total max points possible per day:	8

Within the study's app, the participants can monitor their physical activity data from the FitBit tracker, log their food and engage in social support activities. FitBit app is used for body weight saving and in cohort 2 only, Fitbit nutrition feature is used for diet logging. The procedures for the 5 components are described below

---

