## **Analysis Plan**

### **I. Below details how the outcomes will address the hypotheses being tested:**

We have two main hypotheses in this study. We are examining our outcomes among 240 adults with overweight or obesity and  $\geq 3$  T2DM risk factors.

Hypothesis 1: That the SocialPOD+points group will lose significantly more weight than the SocialPOD-points group.

Hypothesis 2: That the SocialPOD+points group will have greater objectively measured levels of social support provision and receipt than the SocialPOD- group

In order to ensure that each of these hypotheses can be addressed we must measure the following outcomes:

Objective body weight assessments

Objective assessment of social support provision and receipt via the app

Type 2 diabetes risk factors (assessed at baseline, 6 months, and 12 months): body weight, body circumference measures, and blood pressure

Demographic data (race/ethnic group and sex)

These outcomes will help us examine how weight loss and social support provision and receipt may differ between groups.

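### Aim 2 tests support received with a mean rating that the protocol itself classes as perceived support; the scheduled receipt count enters no Aim 2 model

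*Combined protocol and SAP*

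**What the plan says.** The Protocol Synopsis lists Aim 2 among the primary aims. Its hypothesis is that the mLife+points group will have "greater levels of social support provision and receipt (both perceived and received) than the mLife". Perceived and received support are thus both named.

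The Assessments table schedules two separate app measures at 6 and 12 months:

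- "Ratings each participant gives to the social support provided to them after they request support (SS perceived")
- "Total number of times other participants provided support to the individual (SS receipt")

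Part I of the Analysis Plan words Hypothesis 2 as: the points group "will have greater objectively measured levels of social support provision and receipt". Among the outcomes that must be measured it lists "Objective assessment of social support provision and receipt via the app". The bias table in part IV adds, under outcome misclassification, "We are using objective validated measures to assess all primary outcomes".

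Part III is the only place where an Aim 2 model is specified. It regresses two outcomes on treatment group: total points earned, as support provided, and "social support received (mean of ratings of support provided to the individual over the 12 months").

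**The concern.** Part III takes the measure that the Assessments table labels as perceived support and calls it support received. The measure that the table labels as receipt is scheduled but not analysed.

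If the plan is followed as written, a comparison of felt support per response would be reported as the test of support received, in a primary aim. A null result would not show that the arms received equal support. A positive result would not show that receipt rose.

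The rating also exists only for some participants. The points table under Intervention components procedures says that "participants will also rate how supported they felt for each response they receive", so a value depends on requesting help, getting a response and rating it. All of this happens after randomisation. Requesting and thanking carry visible points in one arm only, so who has a rating could differ by arm. Part III does not say what to do with people who have none.

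**Working it through.** **Step 1. Set the passages side by side.**

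| Place | Ratings after a request | Count of support from others |
|---|---|---|
| Assessments table | perceived support | receipt |
| Analysis Plan I, Hypothesis 2 | not named | fits objectively measured receipt |
| Analysis Plan III, Aim 2 model | called support received | absent |

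Neither of the two Aim 2 outcomes in part III is the receipt count. Total points do not fill the gap, because part III defines them as support provided. Part V mentions sub-analyses of provision and receipt by sex and age but names no measure.

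**Step 2. What a mean rating measures.** For participant i with k rated responses and ratings r(1), …, r(k), the outcome is [r(1) + … + r(k)] / k. If k is multiplied by any factor and the ratings keep the same average, the outcome does not change. If k = 0 it is undefined, even for someone who received many thumbs-up or outreach messages, since only responses to requests are clearly rated.

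**Step 3. The plan's own Aim 2 power.** Statistical Design and Power states 99% for app usage and 95% for points earned. The check is power = Φ(d√(n/2) − 1.96), two-sided 0.05, with n per arm.

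- Points: d = 50/105 = 0.476. At n = 120, Φ(0.476 × 7.746 − 1.96) = Φ(1.73) = 95.8%.
- App usage: d = (50.7 − 34.4)/√((25.0² + 25.8²)/2) = 16.3/25.4 = 0.642. Power is 99.9% at n = 120 and 99.5% at n = 100.

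Both stated figures reproduce. Neither concerns receipt. No difference or SD is given for the count or the rating, so power for receipt cannot be derived from the documents.

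**Step 4. Illustration of what the choice could cost.** Every input here except the 120 per arm is an assumption. Counts are gamma-Poisson with mean 5 or 20 in mLife, doubled in mLife+points. The count test is a t test on log(count + 1). Participants are independent and everyone has a rating, which favours the rating. A smaller gamma shape means more dispersion. The standardised difference in log count from simulation is about 0.56, 0.385 or 0.26 at shape 1, 0.5 or 0.25. A rating correlated r with log count carries r times that difference.

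| Gamma shape | Count detects doubling | Rating detects it, r = 0.5 |
|---|---|---|
| 1 | about 99% | about 59% |
| 0.5 | about 85% | about 32% |
| 0.25 | about 50% | about 18% |

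Hand check at shape 0.5: count Φ(0.385 × 7.746 − 1.96) = Φ(1.02) = 85%; rating Φ(0.1925 × 7.746 − 1.96) = Φ(−0.47) = 32%. At shape 1 the rating detects the doubling in about 26% of trials at r = 0.3, and in 5% at r = 0, which is true by construction.

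**Step 5. Missing ratings.** In a null simulation where having a rating depends on a tendency to request help, equal rated shares keep the error near 5%. Assumed shares of 80% v 60% give 9.0–17.2% over correlations from −0.5 to 0.5. The favoured arm reverses with the sign of the correlation. The documents give neither the shares nor the correlation.

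**The case against.** The strongest reply is that part III prints its definition openly, that the synopsis includes perceived support in the hypothesis, and that the rating is therefore a legitimate outcome. That stands for the perceived part. It does not supply a test of the received part, and it does not justify the label.

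Four stronger readings may tempt a reader, and the documents do not support them.

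- *That nobody is told who is analysed for Aim 2.* The intent-to-treat sentence sits in the Aim 1 paragraph, but the heading covers both aims, the next sentence says that models for each primary aim share one form, and part I refers to 240 adults for both hypotheses. Intent-to-treat can reasonably be read as extending to Aim 2. What remains is that a complete-case mean rating would not deliver it.
- *That some randomised people certainly never reach the app.* The Randomization Procedure allocates at 50% of baseline assessments, and only those who complete all components are confirmed for training. Overview of assessments, however, randomises only after all baseline assessments. The two conflict, so the point is open.
- *That the rating comparison is biased in a known direction.* Both arms practise requesting or rating at training, and mLife has a daily checklist, so any difference between arms in who is rated may be small.
- *That the count would have about 99% power.* That figure rests on gamma shape 1 and independent participants.

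The count has its own difficulties, and this part of the objection stands. The documents do not say whether newsfeeds are separate by arm and cohort. If they are, there are four feeds of about 60, and an assumed feed-level log-SD of 0.1 or 0.2 raises the null error of a participant-level count test to about 10–12% or 21–26%. Two feeds per arm are too few to correct this fully. If the arms share a feed, each receives support from the other and the contrast is diluted. Receipt may also not be independent of provision, which is already tested through points. Finally, the count needs a list of which logged acts qualify, since being thanked or replied to could also be counted.

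**Conclusion.** The concern holds as a mismatch between the outcome analysed and the outcome hypothesised. The received part of Hypothesis 2, a primary hypothesis, has no planned test on the measure that the protocol calls receipt, and the measure used in its place is one that the protocol calls perceived. This conclusion rests on the text alone and needs no assumption.

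The consequence cannot be sized from the documents, which give no rated share, no correlation between rating and count, and no count dispersion. The simulated figures are illustrations. In every setting tried the count was the more sensitive measure of a change in amount, but its absolute power varied widely. Aim 1, which set the sample size, is unaffected. This should be fixed before Aim 2 is analysed; it does not undermine the trial as a whole.

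**What to change.** Amend the Aim 2 paragraph in part III of the Analysis Plan as follows.

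1. Make the receipt count from the Assessments table, taken from the app log, the Aim 2 receipt outcome for all randomised participants as assigned, with zero where no support was logged. Name the logged acts that count. Use a count model or robust standard errors. State whether newsfeeds are separate by arm and cohort. If they are, note that participants sharing a feed may not be independent; if the arms share a feed, note that the receipt contrast is diluted.
2. Relabel the mean rating as perceived support. Report the share of participants with a rating by arm, state how those without one are handled, and do not interpret the result as amount received.
3. Note that the stated Aim 2 power covers app usage and points earned only, and that none was calculated for receipt.

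The cost is SAP wording and a little analysis work, since the count is already a scheduled measure; agreeing the list of qualifying acts is the main task. Two limits must be accepted: the stated Aim 2 power does not carry over to receipt, and a receipt finding may not be independent confirmation of a provision finding.
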